#### 6.4 Risks and Benefits

In non-clinical studies, no safety concerns were identified for respiratory function and central nervous system after administration of DNDI-0690. Furthermore, no pharmacological effects on cardiovascular parameters are expected at the doses to be administered in this trial.

Kidney was identified as potential target organ for toxicity in the 28 day DNDI-0690 administration in cynomolgus monkeys. In this study, only single doses will be given, thus, the risk for renal toxicity is considered to be low.

Nevertheless, special attention will be paid to any changes in renal function (creatinine, blood urea nitrogen [BUN], creatinine clearance (CLcr); see Appendix 1). Clinical early renal toxicity biomarkers in plasma and urine may be investigated if changers in renal function are observed. Furthermore, subjects with impaired renal function will be excluded (Section 9.3), and rules for no further dose escalation based on renal function markers are implemented (Section 8.2.1).

According to noteworthy changes observed in DNDI-0690 pivotal toxicity study in cynomolgus monkeys (no significant change was observed in the rat), some biochemistry changes may be anticipated in humans and thus will be monitored accordingly during the clinical trial. Total serum bilirubin, alkaline phosphatase (ALP), glutamate dehydrogenase, cholesterol, aspartate aminotransferase (AST) and alanine aminotransferase (ALT) levels will be especially monitored to assess any effect on liver function.

Changes in the heart in a GLP 4-week study in cynomolgus monkeys were observed, but only in the 2 female monkeys that died at Day 23 and 29. Histological findings suggested that these changes were secondary to agony. The cardiac safety of the subjects will be carefully monitored by holter extracted electrocardiograms (ECGs) as well as safety ECGs and measurement of serum Troponin I concentrations as a cardiac safety marker.

In the 4 week toxicity study in monkeys, effects on the testes (atrophy of the tubular seminiferous epithelium, decrease in tubular size) were observed at 100 and 400 mg/kg per day doses after 28 days of treatment. The overall exposure at which these effects were observed are markedly higher than the expected exposures in humans (after single doses) therefore, the risk for humans is considered to be low in this study. Nevertheless, male study subjects should be informed of potential effects of DNDI-0690 on human fertility, as suggested by the morphological changes observed in the testes of some non-human primates treated in the 4-week toxicology study.

Non-clinical findings for Pretomanid ([S]-PA-824) and Delamanid (Deltyba®, OPC-67683 from Otsuka Pharmaceuticals), two compounds with a high degree of structural similarity to DNDI-0690, potentially reflect some "class effect" as the testis and kidney were also identified as target organs in non-clinical studies.

Administration of Pretomanid or Delamanid in human healthy subjects did not lead to significant side effects and were well tolerated. These data suggest that this class of compound is relatively well tolerated and that clinical monitoring of heart and renal function, together with the other standard measures should ensure the safety of the volunteer subjects during this Single Ascending Dose (SAD) FIH study.

There is no data on interactions with drugs once DNDI-0690 is administered in humans. Whilst no drug to drug reactions are foreseen, the use of prescription medicine is restricted/prohibited except those used to treat AEs as judged by the Investigator or delegate, see Sections 9.3 and 11.4.

No data on reproductive toxicity and embryo-foetal developmental toxicity are available to date. Therefore, WOCBP will be excluded from participating in this study.

Acute toxicity with single DNDI-0690 dosing is not anticipated to pose a risk of concern to healthy volunteers.

Collecting blood samples from a vein may cause pain, swelling, bruising, light-headedness, fainting, and very rarely, clot formation, nerve damage and/or infection at the venepuncture/cannulation site.

During cannulation, more than one attempt may be needed to insert the cannula in a vein of a subject and it is possible that bruising and/or inflammation may be experienced at the site of cannulation.

Electrocardiogram stickers on the subjects' chests and limbs may cause some local irritation and may be uncomfortable to remove but subjects will be closely monitored to ensure any local irritation does not persist.

There is no benefit to the subjects from taking part in this study. The development of a product to improve the treatment of Leishmaniasis will be of benefit to patients with the disease.

The overall risk benefit balance is therefore considered to be acceptable.

## 7 Objectives and Endpoints

#### 7.1 Objectives

#### 7.1.1 Primary Objective

• To assess the safety and tolerability of DNDI-0690 after single oral doses

#### 7.1.2 Secondary Objective

• To investigate plasma and urinary PK of DNDI-0690 after single oral doses

#### 7.1.3 Exploratory Objectives

- To investigate any potential changes to renal toxicity markers in plasma and urine.
- To investigate the metabolite profile of DNDI-0690.
- To assess the effect of DNDI-0690 on Holter ECG parameters.
- To investigate the PK of DNDI-0690 after singles doses in the fed versus fasted state in healthy male subjects
- To investigate the PK of DNDI-0690 after single doses in healthy WONCBP versus healthy male subjects

#### 7.2 Endpoints

#### 7.2.1 Primary Endpoints

• Safety parameters (changes in vital signs, ECG, safety laboratory parameters with special focus on renal function parameters serum creatinine, BUN, and CLcr) and treatment-emergent adverse events (TEAEs).

#### 7.2.2 Secondary Endpoints

- Measurement of the PK parameters AUC0-inf, Cmax, AUC0-inf/D, Cmax/D, AUC0-24, AUC0-inf,norm, AUC0-t, AUC0-t, Cmax,norm, Tmax, T/2, MRT, AUCt-inf, Vz/F, Cl/F, lambda-z and points terminal for DNDI-0690.
- Measurement of the urine PK parameters Ae, Fe and CLr for DNDI-0690.

#### 7.2.3 Exploratory Endpoints

- Changes in clinical early renal toxicity markers in urine: alpha-glutathione Stransferase (α-GST), clusterin (CLU), Cystatin C (CysC), Kidney Injury Molecule-1 (KIM-1), neutrophil gelatinase-associated lipocalin (NGAL), osteopontin (OPN), albumin (ALB) and total protein (TPRO).
- Identification of DNDI-0690 metabolite profile (to be reported separately)
- Analysis of Holter extracted ECGs for the following parameters: RR, heart rate (HR), PR, QRS, QT, corrected QT interval by Fridericia's formula (QTcF), corrected QT interval by Bazett's formula (QTcB), ΔHR, ΔRR, ΔPR, ΔQRS, ΔQT, ΔQTcF and ΔQTcB.
- Comparison of the PK parameters AUC(0-t), AUC(0-inf) and Cmax of DNDI-0690 in the fed state versus fasted state in male subjects
- Comparison of the PK parameters AUC(0-t), AUC(0-inf) and Cmax of DNDI-0690 in WONCBP subjects versus male subjects

## 8 Study Design

#### 8.1 Study Plan

[figure not shown]
This is a single centre, double-blind, randomised, placebo-controlled, parallel-group, single oral dose, dose-escalation study in healthy male and WONCBP subjects. It is planned to enrol 8 subjects in 8 planned cohorts. Cohorts 1 to 7 will include male subjects. Cohort 8 will include WONCBP subjects. Subjects will be randomly assigned to receive a single oral dose of active IMP or matching placebo in a sequential escalating manner with a minimum of 7 days dosing of each cohort.

The planned starting dose for Cohort 1 (Regimen A) will be 10 mg. Doses to be administered in Cohorts 2 to 8 will be determined based on emerging PK and safety data, see Section 8.2.1. Details of the IMPs are provided in Section 5.2.

Each cohort will follow the same study design (Figure 1). Subjects will be screened for inclusion in the study up to 28 days before dosing. Subjects will be admitted during the morning of the day before dosing (Day -1) for all regimens. Subjects will be dosed in the morning of Day 1 in a randomised, double-blind manner with either DNDI-0690 capsule or matching placebo. Subjects in Cohorts 1 to 6 and 8 will be dosed following a minimum overnight fast of 10 h. Subjects in Cohort 7 will be dosed after a standard high-fat breakfast. Subjects will remain onsite until 72 h post-dose. A follow-up visit will take place 7 to 10 days post-dose to ensure the ongoing wellbeing of the subjects. There will be a minimum of 7 days between dosing of each cohort.

As a safety precaution each cohort will be split into two groups: sentinel (2 subjects) and main (6 subjects). The subjects of the sentinel group (1 subject on active, 1 subject on placebo) will be dosed with an appropriate interval between them as allowed by logistics. After review of the safety data from the 24 h post-dose period, the Principal Investigator (PI), or medically-qualified designees who are familiar with the study protocol and Investigator's Brochure (IB), will decide whether to proceed with dosing the remaining subjects in the main group (5 subjects on active treatment, 1 subject on placebo) at least 24 h after the second sentinel subject. The first subject of the main group will be dosed no earlier than 24 h after dosing of the second subject in the sentinel group.

#### Figure 1 Study Sequence

Dose selection for each Regimen B to H, will be made upon review of PK and safety data from preceding cohorts, see Section 8.2.1.

Following the administration of the first 7 regimens (A to G), there will be an interim data review during which the PK and safety data will be reviewed. The decision to proceed with the next regimen will be dependent on the PK and safety data from previous cohorts, see Section 8.2.1.

Full details of the interim data reviews are provided in Section 8.2.

#### 8.2 Criteria for In-Study Decisions

In-study decisions will be made by at a minimum the investigator, the sponsor's project manager and a PK expert and/or the sponsor's medical responsible where appropriate.

#### 8.2.1 Criteria for Dose Escalation

Progression to the next dose group will be permitted after review of safety and PK data suggests that it is safe to do so. Dose increases will only be made after a complete review of all data collected from the previous dose group by a SRC as defined in the SRC charter. The SRC will always comprise at a minimum the investigator, the sponsor's medical responsible and a PK expert where appropriate. Full description of the SRC activities will be part of a SRC Charter implemented before the dosing of the first volunteer.

Each dose cohort will be split into 2 groups, a sentinel group (1 subject on active treatment, 1 subject on placebo), and a main group (5 subjects on active treatment, 1 on placebo). The decision to proceed with the main group will be made by the investigator, based on safety data until 24 h post-dose of the second sentinel subject (see also Section 8.5 for stopping criteria). The investigator will inform the sponsor of any safety concerns.

For dose escalation (or reduction, see below) to proceed, data must be available from a minimum of 6 subjects who have completed the planned safety assessments up to 48 h after dosing and the planned PK assessments up to 48 h after dosing to ensure at least 4 subjects had received active IMP.

The following data are required:

- AEs (mandatory)
- Vital signs
- Safety laboratory, specifically renal function parameters
- ECG
- Physical examinations
- Plasma concentrations of DNDI-0690
- Interim PK parameter estimations: AUC and Cmax

The time points for Troponin I sample collection may be altered based on emerging data from previous cohorts.

Data provided by Quotient Sciences will be provided to the SRC in accordance with the Quotient Sciences standard operating procedure (SOP) on interim dose decision making and dose escalation and as described in the SRC Charter. The decision will be documented and signed by the PI as per Quotient Sciences current SOP and by the DNDi representative as described in the SRC Charter. Evidence of the decision will be retained in the ISF.

Dose escalation will not occur if:

• A serious adverse reaction (ie, a serious adverse event [SAE] considered at least possibly related to the IMP administration) occurs in one subject.

Or

• Severe non-serious adverse reactions (ie, severe non-serious AE considered as, at least possibly related to the IMP administration) occur in two subjects in the same cohort, independent of within or not within the same system organ class.

Or

- If two or more subjects in the pre-ceding dose group experience any of the following:
  - ALT or AST >3x upper limit of normal (ULN) and considered IMP related.
  - Decrease in CLcr below 80 mL/min and judged as clinically significant by the investigator (with reference to the change from baseline value) and considered IMP related.

 an absolute increase in serum creatinine of ≥0.3 mg/dL or ≥ 26.4 µmol/L which is judged as clinically significant and considered IMP related.

Or

- If one or more subjects in the preceding dose group experience:
  - an increase in Troponin I concentration > ULN which is considered clinically significant by the investigator (with reference to the change from baseline value) and considered IMP related.
  - an increase in QTcF value of >60 msec from baseline, confirmed by repeat triplicate measurements or an absolute increase in QTcF >500 msec, confirmed by repeat measurement and considered IMP related.

Or

 if the dose in a single subject is anticipated to exceed an AUC0-24 of ≥100 µg×h/mL. These limits are based on the exposure observed at the 20 mg/kg in cynomolgus monkeys (NOAEL; AUC0-24 of 101 µg×h/mL in male and 111 µg×h/mL in females).

Or

 if the dose in a single subject is anticipated to exceed a Cmax of ≥ 8.0 µg/mL. These limits are based on the exposure observed at the 20 mg/kg in cynomolgus monkeys (NOAEL; Cmax of 8.03 µg/mL in males and 9.03 µg/mL in females).

Dose escalation between cohorts will be limited to a maximal 5-fold increase for the first 3 cohorts and a maximal 3-fold increase thereafter, depending on safety and tolerability data and predicted exposure (both AUC and  $C_{max}$ ).

If this criteria is met, or if it is deemed necessary, the dose selected for the subsequent cohort may be lower than the last as long as the study stopping criteria (Section 8.5) has not been met. The reduced dose level may be an intermediate dose level to those already assessed or may be repetition of a previously administered dose level with the aim to gather further data for that specific dose level. If mild or moderate AEs occur at a particular dose level, that dose level may be repeated, with the aim of further exploring the relationship between dose/exposure and AE. Any decision to investigate an intermediate or reduced dose level will be fully documented.

Following review of safety and PK data and after completion of Cohort 5, the SRC has determined that fed dosing in Cohort 7 and the inclusion of WONCBP in Cohort 8 are required in order to further explore the PK and safety profile of DNDI-0690. The dose in Cohort 7 will not exceed the 1/3 of the maximum tolerated dose in fasted state. The dose in Cohort 8 will not exceed the maximum tolerated dose in males.

This decision will be made based on PK and safety data from preceding cohorts, as outlined above.

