#### 8.3 Subject Withdrawal

If a subject wishes to leave the study at any time, they will be permitted to do so. Every reasonable effort will be made by Quotient Sciences to complete a final assessment/discharge procedures. Quotient Sciences will advise the sponsor of the withdrawal of any subject from the study.

Early withdrawal is defined as the date of the decision to withdraw the subject from the study. Subject completion is defined as the date of the last procedure conducted or last contact (ie phone call) for that subject.

If a subject requests to leave the clinical unit earlier than the planned discharge time eg due to unforeseen personal circumstances, but aims to return to the clinical unit to complete the study, this will be documented as a subject self-discharge and a protocol deviation. The subject must complete the planned assessments/discharge procedures before discharge from the clinical unit and will return for the next assessments, as planned.

Subjects will be withdrawn from the study drug(s) for the following reasons:

- Experiencing a serious or severe AE including but not limited to:
  - QTcF interval of >500 msec or increase in QTcF interval of >60 msec from baseline (confirmed following a repeat ECG after 10 min in resting position)
  - ALT concentration >3 × the upper limit of the reference range (confirmed following a repeat ALT blood test)
- Experiencing a 25% decrease in CLcr
- Pregnancy
- Concurrent illness or requirement for prohibited medication
- At the discretion of the investigator

Subjects will be withdrawn from the study for the following reasons:

- Termination of the study
- Upon the subject's request (withdrawal of consent)
- Significant deviation from the protocol

For the purpose of QTcF withdrawal criteria, baseline will be considered as the average of the pre-dose Day 1 triplicate measurement. For the purpose of CLcr and ALT withdrawal criteria, baseline will be considered as the admission Day -1 measurement.

For a subject who withdraws because of an IMP-related AE, every effort will be made to ensure the subject completes follow-up procedures. Any subject withdrawn or discontinuing the study prematurely because of an IMP-related AE or termination of the study will be considered to have completed the study, and will not be replaced.

Subjects withdrawing for other reasons may be replaced at the discretion of the investigator and sponsor.

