#### 9.2 Inclusion Criteria

- 1. Healthy males (Cohorts 1 to 7) or healthy WONCBP (Cohort 8)
- 2. 18 to 55 years (Cohorts 1 to 7) or 18 to 60 years (Cohort 8) of age at the time of signing informed consent
- 3. Body mass index (BMI) of 18.0 to 30.1 kg/m^2 as measured at screening
- 4. General good physical health determined by medical and surgical history, physical examination, 12-lead ECG, vital signs and clinical laboratory tests

- 5. Normal blood pressure: Systolic blood pressure between ≥90 and ≤140 mmHg, Diastolic blood pressure ≤90 mmHg, measured after 10 min rest in supine position at screening, admission and pre-dose
- 6. A resting HR between ≥40 and ≤90 bpm measured after 10 min rest in supine position at screening, admission and pre-dose
- 7. ECG recording without clinically significant abnormality, including QTcF measure of ≤450 msec (male) or ≤470 msec (female) at screening, admission and pre-dose
- 8. Having had no febrile seizures or infectious illness for at least 7 days prior to administration of the IMP (Day 1)
- 9. Must be willing and able to communicate and participate in the whole study
- 10. Must provide written informed consent
- 11. Must agree to adhere to the contraception requirements defined in Section 9.4 and the life-style restrictions described in Section 9.6

Inclusion criteria 4, 5, 6, 7 and 8 from the list above will be re-assessed at admission/pre-dose.

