#### **13.3 Exploratory Assessments**

#### 13.3.1 Holter extracted ECGs

Continuous Holter monitoring will commence at least 1 h prior to dosing until 24 h post-dose, ie, after the blood sample for PK has been withdrawn at 24 h post-dose. Subjects will be required to be supine for 20 min (10 min rest period, 10 min extraction) prior to the nominal time point where an ECG extraction is scheduled. The extraction will be taken in the 10 min immediately prior to the nominal time point and no other procedures will be performed within this time window. All ECG extractions will occur in triplicate. Values from triplicates (RR, PR, QRS, and QT) will be averaged in order to obtain one single value per time point. On Day 1, three pre-dose triplicates will be extracted and averaged to establish a baseline value.

The recordings will be archived for a maximum of 25 years and analyzed only in case the clinical development of DNDI-0690 progresses to a MAD trial, eg, the Holter extracted ECGs will be analysed together with the Holter extracted ECGs collected in the MAD trial, and reported in a separate report. Holter extraction window times will be recorded in the subject's source. The Holter data collected in this trial will not be part of the trial's clinical data base.

Where any scheduled extractions are missed a protocol deviation will be recorded, loss of leads or interruption of the recording outside of the scheduled extractions will not be considered a protocol deviation.

See Section 10.3.2 for details on timing of Holter extractions in relation to other procedures.

In case the extracted ECG data are analysed, the following analyses are planned and will be reported in a separate report:

Changes from baseline (average of the three pre-dose extracted ECG triplicates) with the extracted ECG triplicates recorded on Day 1 will be calculated for each parameter:

- Categorical analysis for RR, HR, PR, QRS, QT, QTcF, QTcB, ΔHR, ΔRR, ΔPR, ΔQRS, ΔQT, ΔQTcF and ΔQTcB according to the thresholds defined below.
- ECG morphological analysis.

The pre-defined thresholds for the categorical analysis for maximum actual values will be:

- QTc interval > 450 msec (male) / > 470 msec (female)
- QTc interval > 480 msec
- QT/QTc interval > 500 msec

and for maximum changes from baseline:

- ΔQTc interval > 30 msec
- ΔQTc interval > 60 msec

All Holter extracted ECGs parameters and their changes from baseline will be summarised by dose regimen and time-point.

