#### 14.8 ECG Measurements

12-lead ECGs will be measured after the subject has been in the supine position for a minimum of 10 min according to the time schedule presented in Appendix 2. ECGs will be taken in triplicate at pre-dose (for baseline), all post-dose measurements will be taken as a single ECG. The acceptable deviations from the nominal ECG measurement time points are:

- The pre-dose ECG measurements will be taken ≤2 h before dosing
- Post-dose ECG measurements will be taken ± 15 min from the nominal post-dose time point.

• Discharge ECG measurements will be taken ± 1 h from the nominal time point.

If a subject shows an abnormal assessment at any stage, repeat measurements may be made and the abnormality followed to resolution if required. Additional measurements may be taken as deemed necessary by the investigator or sub-investigator. The PI or sub-investigator must double-check the results.

All safety ECG (from baseline to end of study visit) will be sent to the central ECG reading facility (Banook) for review by the cardiologist. A cohort report on ECG findings will be issued for review at the SRC dose-escalation meetings. Measurements will be sent back to Quotient at the end of the study.

Any clinically significant abnormality, including changes from baseline, will be reported as an AE.

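### The one-subject QTcF escalation stop in Section 8.2.1 sets 500 msec as a rise instead of a value, so its absolute limit does no work as printed

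*Protocol*

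**What the plan says.** Section 8.2.1 lists the conditions under which escalation will not occur. One group is triggered by a single subject in the preceding dose group, and its QTcF line has two limbs. The first is a rise of more than 60 msec from baseline, confirmed by repeat triplicate. The second is "an absolute increase in QTcF >500 msec, confirmed by repeat measurement and considered IMP related".

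The protocol uses 500 msec in two other places:

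- Section 8.3, withdrawal from study drug: "QTcF interval of >500 msec or increase in QTcF interval of >60 msec from baseline". Here 500 msec is the interval and 60 msec is the change.
- Section 13.3.1, Holter categories: "The pre-defined thresholds for the categorical analysis for maximum actual values will be" introduces a list that ends with "QT/QTc interval > 500 msec". The separate list for changes from baseline contains only 30 and 60 msec.

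The same list in Section 8.2.1 also has a two-subject criterion that begins "an absolute increase in serum creatinine of ≥0.3 mg/dL", where the same two words describe a genuine change. No other section corrects or redefines the QTcF wording in Section 8.2.1.

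**The concern.** The usual pairing, which Section 8.3 prints correctly, combines a limit on change with a limit on value. The value limit is there for subjects who start high and reach a worrying interval without a large rise. Section 8.2.1 turns the value limit into a second, far larger limit on change, so those subjects are no longer covered by a pre-set rule.

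The error sits in an operative safety rule. Each subject receives one dose, so withdrawal from study drug under Section 8.3 does nothing for the next cohort. Protection of the next cohort has to come through Section 8.2.1. If the printed threshold does not apply, blocking escalation depends on SRC judgement or on the event being classed as serious.

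**Working it through.** No sample size, power or error rate is involved. The check compares the wording and does arithmetic on the thresholds.

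**Inputs**

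| Item | Value | Source |
|---|---|---|
| Escalation stop, limb 1 | rise > 60 msec | Section 8.2.1 |
| Escalation stop, limb 2 as printed | rise > 500 msec | Section 8.2.1 |
| Withdrawal limit | value > 500 msec or rise > 60 msec | Section 8.3 |
| Highest eligible QTcF, including pre-dose | 450 msec (men), 470 msec (women) | Section 9.2, criterion 7 |
| Baseline | mean of the pre-dose Day 1 triplicate | Section 8.3 (stated for withdrawal); Section 14.8 |

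Let B be baseline, Q the post-dose QTcF, and Δ = Q − B.

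**Step 1. Does printed limb 2 add anything?** Δ > 500 implies Δ > 60. On magnitude, limb 2 is a strict subset of limb 1, so the two limbs together reduce to Δ > 60. They differ only in how the finding is confirmed (repeat triplicate versus repeat measurement).

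**Step 2. What would limb 2 require?** From the highest eligible male baseline, limb 2 needs Q > 450 + 500 = 950 msec. Limb 1 is met once Q > 450 + 60 = 510 msec.

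**Step 3. Which men meet the Section 8.3 limit but neither printed limb?** They need Q > 500 and Q − B ≤ 60.

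- Lower bound on baseline: B ≥ Q − 60 > 500 − 60 = 440 msec.
- Upper bound on the value: Q ≤ B + 60 ≤ 450 + 60 = 510 msec.

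The gap is therefore 440 < B ≤ 450 with 500 < Q ≤ 510. At a baseline of 440 msec or lower, any value above 500 msec is already a rise of more than 60 msec and limb 1 catches it.

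**Step 4. Example.** B = 448, Q = 505: Δ = 505 − 448 = 57 msec. Section 8.3 is met (505 > 500). Limb 1 is not met (57 ≤ 60), and printed limb 2 is not met (57 ≤ 500). With limb 2 as a value limit, 505 > 500 triggers the stop.

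**Step 5. Women.** The same arithmetic with a cap of 470 msec gives values up to 470 + 60 = 530 msec. This is not counted, because Cohort 8 is the last planned cohort and no escalation follows it.

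**Step 6. Do other rules close the gap?**

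- Section 8.5 has no QTcF criterion.
- Severe non-serious reactions block escalation only when two subjects in the same cohort have them.
- One serious reaction does block escalation, but that rests on the seriousness and causality assessments, not on a number.
- The general rule, "Progression to the next dose group will be permitted after review of safety and PK data suggests that it is safe to do so", is a judgement by the SRC.

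**The case against.** The strongest reply is that nobody would apply the literal reading. It demands a QTcF above 950 msec, and Section 8.3 prints the same 500/60 pair correctly. The grammar also points to a value. The true changes in the list are written as an increase *of* an amount, and limb 1 adds the reference to baseline; the disputed limb has neither. It resembles the Troponin I line just above it, where an increase beyond the upper limit of normal plainly means a rise to above a level.

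The reply continues that escalation is never automatic. ECG data are among the data required for the decision, and Section 14.8 adds central cardiology reading: "A cohort report on ECG findings will be issued for review at the SRC dose-escalation meetings". A case judged serious and related would stop escalation and halt the study.

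The remaining reach is also small. Section 8.2.1 records that Cohort 5 is complete. It caps Cohort 7 at one third of the fasted maximum tolerated dose and Cohort 8 at the male maximum tolerated dose. That leaves roughly one step, to Cohort 6, that could exceed doses already given. Finally, Section 13.3.1 is an exploratory reporting threshold for recordings that may never be analysed.

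Much of this stands. The intent can be inferred, the gap is narrow, and Section 13.3.1 only shows how the protocol uses the number; it is not a competing limit. The operative conflict is with Section 8.3.

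It does not repair the rule. The creatinine line uses the same two words for a change, so the list does not explain itself. SRC review is discretionary, whereas this list exists to fix limits in advance. The decisions for Cohorts 7 and 8 are still referred back to Section 8.2.1.

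**Conclusion.** The concern holds. Section 8.2.1 misstates a one-subject escalation threshold and disagrees with Section 8.3. As printed, the 500 msec limb contributes no threshold of its own.

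The practical size is small: men with a baseline above 440 and up to 450 msec whose confirmed, IMP-related QTcF is above 500 and up to 510 msec. That range assumes that baseline is the pre-dose triplicate mean, which Section 8.3 states for withdrawal and Section 8.2.1 does not restate. It also assumes that the 450 msec eligibility cap applies to that mean.

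The SRC would probably apply the intended meaning, so this does not threaten the trial. It should still be corrected, because the error lies in a safety rule whose purpose is to leave nothing to interpretation.

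**What to change.** In Section 8.2.1, reword the second QTcF limb as: *an absolute QTcF value >500 msec, confirmed by repeat measurement and considered IMP related*. Use the same words in the SRC charter if it repeats the rule.

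The confirmation steps in Sections 8.2.1 and 8.3 need not be made identical. The cost is one phrase in a protocol amendment and, where needed, one in the charter. No procedure, analysis or sample size changes.
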